10.7. Analysis of demographics

Demographic characteristics (center, age at study vaccination in years, gender, ethnicity, geographic ancestry, history of influenza vaccination since the 2014/2015 season) and withdrawal status will be summarized by group in the ES, using descriptive statistics:

- Frequency tables will be generated for categorical variable such as center.
- Mean, median, standard deviation will be provided for continuous data such as age.

10.8. Analysis of safety

The analysis will be performed on the ES.

All analyses will be descriptive. Data will be presented by dose, overall/dose and overall/subject. Outputs will be presented by study group. Analyses will be repeated pooling groups according to the adjuvant (AS01, AS03, no adjuvant).

- The percentage of subjects with at least one local AE (solicited and unsolicited), with at least one general AE (solicited and unsolicited) and with any AE during the solicited follow-up period will be tabulated with exact 95% CI. The same calculations will be performed for AEs rated as grade 3.
- The percentage of subjects reporting each individual solicited local and general AE during the solicited follow-up period will be tabulated with exact 95% CI. The same tabulation will be performed for grade 3 AEs and for AEs with relationship to vaccination.
- The verbatim reports of unsolicited AEs will be reviewed by a physician and the signs and AEs will be coded according to the Medical Dictionary for Regulatory Activities (MedDRA). The percentage of subjects with at least one report of unsolicited AE classified by the MedDRA and reported up to 28 days after vaccination will be tabulated with exact 95% CI. The same tabulation will be performed for grade 3 unsolicited AEs and for unsolicited AEs with a relationship to vaccination.
- The percentage of subjects with MAE(s) will be summarized by group with exact 95% CI.
- The percentage of subjects with episode(s) of ILI will be summarized by group with exact 95% CI. **(Amended: 11 July 2019)**
- At each hematology/biochemistry sampling timepoint, by study group, individual hematological and biochemical values will be presented as number of subjects out of range (above and below normal range) and tabulated by toxicity grading (refer to [APPENDIX C](#)). In addition, changes from baseline (median/interquartile range) will be presented.
- SAEs and pIMDs will be described in detail. Withdrawals due to (S)AEs will also be summarized.

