Therefore, the vaccine regimen in the SUIV groups will consist of sequential primary intramuscular immunization with one dose (Day 1) or 2 doses (Day 1 and Day 57) followed by a booster dose at Month 14 of a vaccine containing split inactivated influenza virus expressing a chimeric HA with at each dose the same stalk domain (H1 stalk) but a different exotic head. The SUIV vaccine will be adjuvanted with AS03_A or AS01_E or non-adjuvanted. The interval of two months between the two priming doses was selected to ensure optimal priming in a setting where the vaccine can be administered the whole year round without time pressure for completion of vaccination in contrast with a seasonal or pandemic influenza vaccination setting. The booster dose at Month 14 is anticipated to be necessary to obtain an adequate and persisting anti-stalk antibody response. In the control group, subjects will be administered one dose of *Fluarix Quadrivalent* inactivated influenza vaccine (IIV4) on Day 1 and then re-vaccinated at Month 14 with the next year’s formulation.

The main purpose of this study will be to assess the safety and the reactogenicity of each SUIV compared to IIV4. This study will also evaluate the adjuvant effect of AS03_A and AS01_E on the immune response when compared to the non-adjuvanted formulation. In addition, the immune response after 1 priming dose and after 2 priming doses will be evaluated, as well as the immune response after a booster dose given 14 or 12 months after a one dose priming schedule or a 2-dose priming schedule, respectively. Since the vaccine sequence of the priming dose and the booster dose in the one dose-priming schedule groups varies, the effect of the chimeric HA vaccine sequence on the humoral immune response will also be assessed. Finally, the cell-mediated immune response and the protective effect *in vivo* of the anti-stalk antibodies will be explored. Passive surveillance will be put in place in order to capture the occurrence of *influenza-like illnesses* during the entire study period. (Amended: 11 July 2019)

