3. STUDY DESIGN OVERVIEW

Figure 1 Study design overview

*If a subject presents signs and symptoms of influenza-like illness (ILI) (see Section 5.4.2), nasal and throat swabs will be collected as soon as possible (preferably within 24 hours, but not later than 7 days) after the onset of an ILI to test for influenza and/or other respiratory pathogens by RT-PCR if deemed necessary or for storage. (Amended: 11 July 2019)

**IDMC reviews will be performed throughout the study (refer to Section 8.8).

Protocol waivers or exemptions are not allowed unless necessary for the management of immediate safety concerns. Therefore, adherence to the study design requirements, including those specified in the outline of study procedures (Section 5.5), are essential and required for study conduct.

- **Experimental design:** Phase I/II, observer-blind, randomized, controlled, multi-centric study with 10 parallel groups.
- **Duration of the study:**
 - Epoch 001: Screening (Day -28 to -2) – only for Phase I subjects (refer to the [Enrolment](#) section).
 - Epoch 002: Primary starting at Visit 1 (Day 1) and ending at Visit 7 (Month 8).
 - Epoch 003: Booster starting at Visit 8 (Month 14) and ending at Visit 12 (Month 26).
- **Primary Completion Date (PCD):** Visit 12 (Month 26).
Refer to [glossary of terms](#) for the definition of PCD.
- **End of Study (EoS):** Last testing results released of samples collected at Visit 12 (Month 26).
Refer to [glossary of terms](#) for the definition of EoS.
- **Study groups:**
 - **cH8/P/cH5-AS03 group:** subjects receiving one dose of cH8/1N1+AS03 at Day 1, one dose of PBS at Day 57 and one booster dose of cH5/1N1+AS03 at Month 14.
 - **cH5/P/cH8-AS03 group:** subjects receiving one dose of cH5/1N1+AS03 at Day 1, one dose of PBS at Day 57 and one booster dose of cH8/1N1+AS03 at Month 14.
 - **cH8/5/11-AS03 group:** subjects receiving one dose of cH8/1N1+AS03 at Day 1, one dose cH5/1N1+AS03 at Day 57 and one booster dose of cH11/1N1+AS03 at Month 14.
 - **cH8/P/cH5-AS01 group:** subjects receiving one dose of cH8/1N1+AS01 at Day 1, one dose of PBS at Day 57 and one booster dose of cH5/1N1+AS01 at Month 14.
 - **cH5/P/cH8-AS01 group:** subjects receiving one dose of cH5/1N1+AS01 at Day 1, one dose of PBS at Day 57 and one booster dose of cH8/1N1+AS01 at Month 14.
 - **cH8/5/11-AS01 group:** subjects receiving one dose of cH8/1N1+AS01 at Day 1, one dose cH5/1N1+AS01 at Day 57 and one booster dose of cH11/1N1+AS01 at Month 14.

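### Pooling the safety tables by adjuvant puts 94 PBS and 47 active injections into each pooled Dose 2 summary, so those rows do not describe a second vaccine dose

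*Protocol*

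**What the plan says.** Section 10.8 sets three levels of safety summary: "Data will be presented by dose, overall/dose and overall/subject". The main layout follows: "Outputs will be presented by study group". The pooled repeat comes next: "Analyses will be repeated pooling groups according to the adjuvant (AS01, AS03, no adjuvant"). The unit being pooled is the study group, and nothing in the section treats Dose 2 differently.

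Section 3 defines what each group receives. In the AS03 family:

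- cH8/P/cH5-AS03: "subjects receiving one dose of cH8/1N1+AS03 at Day 1, one dose of PBS at Day 57"
- cH5/P/cH8-AS03: "subjects receiving one dose of cH5/1N1+AS03 at Day 1, one dose of PBS at Day 57"
- cH8/5/11-AS03: "subjects receiving one dose of cH8/1N1+AS03 at Day 1, one dose cH5/1N1+AS03 at Day 57"

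The AS01 and non-adjuvanted families follow the same pattern, and Table 17 confirms it. IIV4 subjects also receive PBS at Day 57. At Day 1 and Month 14 every group receives an active vaccine.

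Section 1.2.2 sets the context: "The main purpose of this study will be to assess the safety and the reactogenicity of each SUIV compared to IIV4". The primary objective (section 2.1) and the primary endpoints (section 10.1) are framed by dose and by group, not by pool.

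**The concern.** A row labelled AS03 or AS01, Dose 2, will be read as the tolerability of a second adjuvanted injection. Under the stated rule most of the injections in that row are PBS. The pooled table also has the larger denominator and narrower interval, so a reader may prefer it to the study-group rows and conclude that a second adjuvanted dose is much better tolerated than it is.

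The overall/dose summaries have a milder form of the same problem, and there it does not depend on pooling. A regimen with one PBS injection out of three will show a lower per-injection rate than a regimen with none, even if the active vaccines are equally reactogenic.

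**Working it through.** **Inputs from the protocol.** Ten groups of 47 (section 4.1). Three groups per adjuvant pool, with products by dose as in section 3 and Table 17. Safety is analysed on the Exposed Set (section 10.8), so the planned 47 per group applies.

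**Check of the pool structure.** Table 28 gives 129 evaluable subjects per pool and 387 in all. 3 × 43 = 129 and 9 × 43 = 387, so both are reproduced, and each pool is three whole groups. The protocol gives no figure for the PBS share.

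**PBS share per pool, on planned numbers.**

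- Dose 2: 3 × 47 = 141 injections. PBS 2 × 47 = 94 (66.7%); active 47 (33.3%).
- All three doses: 9 × 47 = 423 injections. PBS 94 (22.2%); active 423 − 94 = 329.
- Dose 1 and booster: no PBS.

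**Effect on the pooled Dose 2 rate.** Let a be the rate after active vaccine and p the rate after PBS.

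- Pooled rate = (a + 2p)/3.
- Excess over PBS = (a + 2p)/3 − p = (a − p)/3, one third of the true excess whatever the rates.
- Relative fall in the rate = 1 − (a + 2p)/(3a) = (2/3)(1 − p/a), which equals two thirds only when p = 0.

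The protocol gives neither a nor p. Assumed ranges are 60-90% for active vaccine and 10-30% for PBS:

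| a | p | Pooled Dose 2 rate | Relative fall |
|---|---|---|---|
| 90% | 10% | 36.7% | 59% |
| 90% | 30% | 50.0% | 44% |
| 80% | 10% | 33.3% | 58% |
| 80% | 20% | 40.0% | 50% |
| 60% | 10% | 26.7% | 56% |
| 60% | 30% | 40.0% | 33% |

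If PBS rates are the same in all pools, the difference between an adjuvanted pool and the non-adjuvanted pool at Dose 2 also shrinks to one third.

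**Illustration with intervals (a = 80%, p = 10%).** In the cH8/5/11 group alone: 38/47 = 81%, exact 95% CI 67-91%. In the pool: (38 + 9)/141 = 47/141 = 33%, exact 95% CI 26-42%. The pooled interval is narrower but estimates a different quantity, and the two intervals do not overlap.

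**Overall/dose, same assumed rates.**

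- Adjuvant pool: (7a + 2p)/9 = (5.6 + 0.2)/9 = 64%.
- One-priming-dose group: (2a + p)/3 = (1.6 + 0.1)/3 = 57%, because 47 of its 141 injections are PBS.
- cH8/5/11 group: 80%, with no PBS.

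Two regimens whose active doses are equally reactogenic would thus show 57% and 80%. IIV4 has the same one-third PBS share as the six one-priming-dose groups.

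**The case against.** The strongest reply is that nothing primary is affected. A reader might infer that the primary Dose 2 reactogenicity result is diluted. The protocol does not support that: objective, endpoints and main output are by study group, each group receives a single product at Day 57, and the cH8/5/11 Dose 2 rows contain active vaccine only. The pooled tables are a descriptive repeat. Holding rules 2a-2c are assessed within an investigational group, so the pool triggers none of them. All of this stands.

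A reader might also infer that the Dose 2 rate falls by two thirds. Two thirds is the PBS share, and the loss in the excess over PBS. The rate falls that far only if PBS recipients report no reactions.

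Section 10.5.1 can be cited as a safeguard, since it analyses the Exposed Set by the treatment actually given and PBS is listed as a treatment of its own in Tables 16 and 17. But PBS at Day 57 is the planned treatment of these groups. Classifying subjects by what they received leaves them in the same group, and section 10.8 then pools that group. At best the two sections are unclear when read together.

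A statistical analysis plan might settle the table layout. However, the protocol is not silent here: it states a pooling rule, and that rule gives the mixed rows.

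It is also fair that pooled Dose 1 and booster rows are clean, that the PBS share is equal across the three pools, and that six of the nine investigational groups have the same PBS share as IIV4 in overall/dose. These points limit the effect but do not make the pooled Dose 2 row a valid summary of a second vaccine dose.

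**Conclusion.** The point holds for the pooled Dose 2 summaries and for the overall/dose summaries. As worded, section 10.8 gives pooled Dose 2 rows that are 94/141 PBS and pooled overall/dose rows that are 94/423 PBS. The excess over PBS at Dose 2 is cut to one third regardless of the rates. The fall in the rate itself, roughly 33-59%, rests on the assumed 60-90% and 10-30%. Counts are planned numbers and assume full dosing.

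Study-group Dose 2 results and the holding rules are intact. Study-group overall/dose figures remain hard to compare across regimens, because they are one third PBS in seven groups (the six one-priming-dose groups and IIV4) and contain none in the three cH8/5/11 groups.

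This is a correction to supplementary descriptive tables and to one summary level of the main tables, not a flaw in the primary safety assessment.

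**What to change.** Amend section 10.8 in three places:

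1. Define the pools by the product injected at each dose. The pooled Dose 2 rows then use only the cH8/5/11 groups, 47 subjects per adjuvant category.
2. Show PBS at Day 57 as its own column, covering the one-priming-dose groups and IIV4.
3. Compute overall/dose on active doses only, in the pooled and the study-group tables: 329 of 423 injections per pool, and 94 of 141 in each one-priming-dose group and in IIV4.

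The change is table wording and needs no new data. The cost is that the pooled Dose 2 denominator drops from 141 to 47 and its interval widens, and the row then repeats the cH8/5/11 study-group row. That denominator is the true exposure to a second active dose. Adding differences from IIV4 with confidence intervals would be a separate request and is not needed for this correction.

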 - Blood samples for passive transfer experiment in animals will be drawn from all subjects at Days 1 (Visit 1), 85 (Visit 6), Month 14 (Visit 8)*.

- Blood samples for cell-mediated immunity (CMI) assessment will be drawn from a sub-cohort of ~225 subjects at Days 1 (Visit 1), 8 (Visit 2), 29 (Visit 3), 64 (Visit 5), 85 (Visit 6), Month 14 (Visit 8)*, Month 14 + 7 days (Visit 9)*, **and** Month 14 + 28 days (Visit 10)*. The sub-cohort will consist of the first Phase II subjects enrolled in pre-specified centers.
- During the entire study period, nasal and throat swabs will be collected as soon as possible (preferably within 24 hours, but not later than 7 days) after the onset of an influenza-like illness (ILI) to test for influenza and/or other respiratory pathogens by RT-PCR **if deemed necessary, or stored for future research.**

**Note that samples already collected for these timepoints by the time of Protocol Amendment 4 implementation at site will not be tested and will be stored, unless deemed necessary based on medical review of the cases.*

- **ILI surveillance:** ILI is defined as at least one of these systemic symptoms:
 - Temperature (oral) $\geq 37.8^{\circ}\text{C}/98.6^{\circ}\text{F}$ and/or,
 - Myalgia (widespread muscle ache);AND at least one of these respiratory symptoms:
 - Cough and/or,
 - Sore throat.Passive surveillance will be carried out from Visit 1 (after Dose 1) until the end of the study (Visit 12). Subjects will be instructed to contact the investigator/study staff as soon as they experience ILI symptoms.
- **Type of study:** self-contained.
- **Data collection:** electronic Case Report Form (eCRF).
- **Safety monitoring:** an Independent Data Monitoring Committee (IDMC) consisting of clinical experts and a biostatistician, independent from the Sponsor, will review unblinded safety data (including laboratory assessment) at a regular frequency to monitor the safety of the subjects throughout the study.

- **Enrolment:** the study will follow a staggered enrolment with 2 steps; the first being Phase I (N = ~80) and the second being Phase II (N = ~390):

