4.2. Inclusion criteria for enrolment

Deviations from inclusion criteria are not allowed because they can potentially jeopardize the scientific integrity, regulatory acceptability of the study or subject safety. Therefore, adherence to the criteria as specified in the protocol is essential.

All subjects must satisfy ALL the following criteria at study entry:

- Subjects who, in the opinion of the investigator, can and will comply with the requirements of the protocol (e.g. completion of the diary cards, return for follow-up visits, contact the site in case of ILI).

Please refer to the [glossary of terms](#) for the definition of ILI.
- Written informed consent obtained from the subject prior to performing any study specific procedure.
- A male or female between, and including, 18 and 39 years of age at the time of the first vaccination.
- Healthy subjects without acute or chronic, clinically significant pulmonary, cardiovascular, hepatic or renal functional abnormality, as established by medical history and clinical examination before first vaccination and laboratory screening tests (the latter being only applicable for subjects enrolled in Phase I).
- Subjects with no history of influenza vaccination within 6 months prior to first study vaccination and who are willing to forego any influenza vaccination during the entire study period.
- Female subjects of non-childbearing potential may be enrolled in the study.
 - Non-childbearing potential is defined as pre-menarche, current bilateral tubal ligation or occlusion, hysterectomy, bilateral ovariectomy or post-menopause.

Please refer to the [glossary of terms](#) for the definition of menarche and menopause.

- Female subjects of childbearing potential may be enrolled in the study, if the subject:
 - Has practiced adequate contraception for 30 days prior to first vaccination, and
 - Has a negative pregnancy test on the day of vaccination, and
 - Has agreed to continue adequate contraception during the entire treatment period and for 2 months after completion of the vaccination series (last vaccination at Month 14).

Please refer to the [glossary of terms](#) for the definition of adequate contraception.

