 - Residents of nursing homes and other long-term care facilities;
 - American Indians/Alaska Natives; and
 - Persons who are extremely obese (Body Mass Index ≥ 40).

Additional criterion applicable for Phase I subjects:

- Hematological and/or biochemical parameters (complete blood cell count [red blood cells, white blood cells], white blood cells differential count [lymphocytes, neutrophils and eosinophils], platelets count or hemoglobin level, creatinine or blood urea nitrogen) outside the laboratory normal ranges, unless the laboratory abnormalities are considered not clinically significant by the investigator.
- Liver enzymes (alanine aminotransferase [ALT] or aspartate aminotransferase [AST]) outside of the normal laboratory ranges.

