10. STATISTICAL METHODS

10.1. Primary endpoints

Reactogenicity and safety

- Occurrence of solicited local and general AEs after each vaccination:
 - Occurrence of solicited local AEs during a 7-day follow-up period (i.e. on the day of vaccination and 6 subsequent days) after each vaccine dose, in all vaccine groups.
 - Occurrence of solicited general AEs during a 7-day follow-up period (i.e. on the day of vaccination and 6 subsequent days) after each vaccine dose, in all vaccine groups.
- Occurrence of unsolicited AEs after each vaccination:
 - Occurrence of unsolicited AEs during a 28-day follow-up period (i.e. on the day of vaccination and 27 subsequent days) after each vaccine dose, in all vaccine groups.
- Occurrence of hematological and biochemical laboratory abnormalities after each vaccination:
 - Any hematological (red blood cells, white blood cells and differential count, platelets count and hemoglobin level) or biochemical (alanine aminotransferase, aspartate aminotransferase, creatinine, blood urea nitrogen [BUN] and BUN-to-creatinine ratio) laboratory abnormality at each visit subsequent to Day 1, in all vaccine groups.
- Occurrence of MAEs, pIMDs and SAEs:
 - Occurrence of MAEs, pIMDs and SAEs throughout the entire study period, in all vaccine groups.

Immunogenicity

Anti-H1 stalk immune response measured by ELISA and by MN assay 28 days after each priming dose:

- Levels of anti-H1 stalk antibody titers by ELISA and by MN assay.

The following aggregate variables will be calculated for the above parameters with 95% confidence interval (CI):

- Seropositivity rates and geometric mean titers (GMTs) at Days 1, 29 and 85.

- Percentage of subjects with a \geq 4-fold increase from Day 1 to Days 29 and 85.
- Percentage of subjects with a \geq 10-fold increase from Day 1 to Days 29 and 85.
- Mean geometric increase (MGI) from Day 1 to Days 29 and 85.

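### The primary laboratory endpoint counts every abnormal value at visits after Day 1, whatever the pre-vaccination value, so new and pre-existing abnormalities are mixed

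*Protocol*

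**What the plan says.** Section 10.1 (repeated in the synopsis) heads the endpoint "Occurrence of hematological and biochemical laboratory abnormalities after each vaccination". The definition beneath it is any haematological or biochemical "laboratory abnormality at each visit subsequent to Day 1, in all vaccine groups", with no condition on the Day 1 result.

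Section 10.8 gives the analysis. It opens "At each hematology/biochemistry sampling timepoint, by study group", and says that "individual hematological and biochemical values will be presented as number of subjects out of range (above and below normal range") and tabulated by toxicity grade. The bullet ends: "In addition, changes from baseline (median/interquartile range) will be presented".

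On entry, section 4.2 relies on history, examination and "laboratory screening tests (the latter being only applicable for subjects enrolled in Phase I"). The Enrolment text in section 3 gives the phase sizes: "the first being Phase I (N = ~80) and the second being Phase II (N = ~390"). In section 4.3, Phase I subjects with haematology, creatinine or urea nitrogen out of range are excluded "unless the laboratory abnormalities are considered not clinically significant by the investigator"; ALT and AST must be in range without that exception.

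A safety blood sample is scheduled at Day 1 for everyone. Footnotes to Tables 5 and 6 place it before vaccination. It is omitted only for Phase I subjects screened less than a week earlier, who then have a recent screening value.

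**The concern.** The heading promises incidence after vaccination; the definition and tables deliver prevalence at each later visit. A subject with a stable, long-standing abnormality can appear in the table at each of the 11 scheduled visits after Day 1 (Visits 2 to 12) without anything having happened after a dose. The samples at Visits 4 and 8, drawn before Dose 2 and the booster, also fall under the definition, so it does not tie an abnormality to the dose it follows.

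This also sits awkwardly with the protocol's own adverse event rules. Section 8.1.1 keeps pre-existing conditions out of the adverse event definition, and section 8.1.5 asks for significant worsening before a clinically significant abnormality present at baseline is reported. The primary laboratory endpoint has no equivalent rule.

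At stake is how the laboratory table of a first-phase safety study reads. In groups of 47, a few carried-over abnormalities can be a large part of a small count, and can hide or mimic a signal.

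**Working it through.** The protocol states no figure for this endpoint, so there is none to reproduce. It also gives no background abnormality rate; the rates below are assumptions, shown as ranges.

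**1. How many subjects lack laboratory screening.** 390 / 470 = 83%, or about 39 of 47 per group.

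**2. Expected number abnormal at Day 1, per parameter and group.** With n = 47 and a proportion b out of range, the expected count is 47b and its binomial SD is √(47b(1−b)).

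| b (assumed) | Expected of 47 | SD |
|---|---|---|
| 1% | 0.47 | 0.68 |
| 2.5% | 1.18 | 1.07 |
| 5% | 2.35 | 1.49 |

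**3. Share of a later count that is pre-existing.** Let s be the chance that a Day 1 abnormality is still present at the visit, and i the chance that a subject normal at Day 1 is newly abnormal. Then counted = bs + (1−b)i, new = (1−b)i, and the pre-existing share = bs / [bs + (1−b)i].

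| b | s | i | Counted | New | Pre-existing share |
|---|---|---|---|---|---|
| 1% | 0.3 | 5% | 5.25% | 4.95% | 6% |
| 1% | 0.3 | 2% | 2.28% | 1.98% | 13% |
| 5% | 0.6 | 5% | 7.75% | 4.75% | 39% |
| 5% | 0.6 | 2% | 4.9% | 1.9% | 61% |
| 5% | 0.9 | 2% | 6.4% | 1.9% | 70% |

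**4. Effect on a comparison of two groups.** Take b = 5% and s = 0.6 in both groups, with new-onset rates of 5% and 2%. The counted proportions are 7.75% and 4.9%. Their difference is 2.85 points, close to the true 3 points (the factor is 1−b = 0.95). Their ratio is 7.75 / 4.9 = 1.58, against 4.75 / 1.9 = 2.5 for new abnormalities. With equal backgrounds, no group is favoured: each rate is inflated and the ratio is pulled towards 1. Chance differences in Day 1 status, on the scale of the SDs in step 2, add noise.

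**5. Whether the planned baseline outputs resolve it.** Suppose 3 of 47 are out of range at Day 1 and 3 of 47 at Day 8. The same two counts fit no new cases (the same three subjects) or three new cases (three different subjects). The median and interquartile range of change describe the middle of the group, so they do not settle it either. Only cross-classifying each subject's later value by the Day 1 value does.

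**The case against.** The strongest reply has four parts.

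- **Shift tables usually belong in the statistical analysis plan.** That plan is not shown, and the lack of a shift table in the protocol is not in itself a fault. What stands is that the protocol does fix this endpoint and its tabulation, and the heading and definition disagree.
- **Baseline is not ignored.** Day 1 is itself a tabulated timepoint, so a group imbalance at entry would be visible, and changes from baseline are presented. This stands at group level; it does not identify new cases.
- **New findings are caught elsewhere.** Clinically significant findings, including baseline ones that significantly worsen, are reported as adverse events (section 8.1.5), and Appendix C also grades haemoglobin on change from baseline. This stands, but it leaves the out-of-range and graded counts for the other parameters as they are.
- **Nothing is tested.** Section 10.8 makes all safety analyses descriptive, randomisation balances background abnormality in expectation, and the IIV4 group shows the background rate. Section 4.3 also excludes chronic renal, hepatic, haematologic and metabolic disorders in both phases, which may keep that rate low. This stands and limits the harm.

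A reader might go further and infer that about half of each group is abnormal at entry, since 1 − 0.95^13 = 49% for the 13 measured parameters. The documents do not support using that figure. It assumes 5% per parameter and independence, although leukocytes and their differential counts are related; at 1% per parameter it is 12%. The protocol plans tables by individual parameter, not a count of subjects with any of the 13.

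**Conclusion.** The point holds as a mismatch between what the primary laboratory endpoint is called and what is counted. New abnormalities are in the counts but are not separated from old ones. Both phases are affected, Phase II more so because it has no laboratory screening.

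The consequence is inflated within-group rates and added noise. A reader might infer that the endpoint fails to measure occurrence at all, or that group comparisons are biased. Neither follows: new cases are counted, and allocation is randomised.

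The size is uncertain. At an assumed 1% to 5% out of range, about 0.5 to 2.4 of 47 subjects per group and parameter are abnormal at Day 1. In the scenarios shown, 6% to 70% of those counted at a later visit were already abnormal; carry-over outweighs new onset only at the higher background rates with low new onset. The change is worth making because the data needed are already collected.

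**What to change.** In sections 10.1 and 10.8, keep the planned all-values tables and add the following.

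1. For each parameter and each visit after Day 1, tabulate range status and toxicity grade by Day 1 status, using the screening value where Day 1 was not drawn.
2. Report subjects with a new abnormality, or a higher grade than at Day 1, as the occurrence after vaccination.
3. For visits after Dose 2 and after the booster, tabulate also against the pre-dose Day 57 and Month 14 values. Comparison with Day 1 alone does not isolate what arose after a later dose.
4. Do not count the pre-dose Day 57 and Month 14 samples as occurring after the dose given at that visit; they belong to the follow-up of the preceding dose.

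The Day 85 interim results have already been reviewed, so label this as an added analysis. Section 10.11 in any case asks for changes to the statistical plan to be described and justified in the study report. Beyond the wording, the cost is programming only: no new samples, visits or subjects are needed.
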